Methodology/Study Design	
Study 048 is a Phase 2, open-label study to evaluate safety, tolerability, and PK of ataluren in male children with nmDMD aged \geq6 months to $<$2 years of age treated TID for 24 weeks with orally administered ataluren 10, 10, 20 mg/kg (morning, mid-day, and evening dose, respectively).
 
Safety evaluations will include TEAEs, serious adverse events (SAEs), adverse events (AEs) leading to discontinuation, laboratory evaluations, EGCs, vital signs, and physical examination.
 
The study will include 3 PK profile assessments (baseline, Week 4, and end of treatment at Week 24). At these visits, PK parameters will be investigated based on blood sampling at pre-dose, and 1-, 2-, 3-, and 4-hours post-dose following both the morning and mid-day ataluren doses, and immediately pre-dose, and 1-, 2-, 3-, 4- and 12- (before the next day morning dose) hours post-dose following the evening dose.
 
The PK parameters, including AUC_{0-24} and $AUC_{0-\tau}$, T_{max}, C_{max}, C_{trough} will be assessed after each dose. If feasible, apparent clearance (CL/F), and $T_{1/2}$ will also be assessed after each dose.

Main Inclusion Criteria	
1. Signed and dated informed consent document indicating that the parent(s)/caregivers(s) of the subject has been informed of all pertinent aspects of the study prior to initiation of any study-related procedures.2. Males \geq6 months to $<$2 years of age.3. Body weight \geq7.5 kg4. Willingness and ability of the subject's parent/caregiver to comply with scheduled visits, drug administration plan, study procedures, and study restrictions.5. Diagnosis of Duchenne muscular dystrophy (DMD) based on an elevated serum CK and genotypic evidence of dystrophinopathy.6. Documentation of the presence of a nonsense mutation of the dystrophin gene as determined by gene sequencing confirmed by a PTC Therapeutics (PTC) designee is required prior to enrollment.

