2.2.2. Secondary Endpoint

The secondary endpoint of this study is the evaluation of PK parameters after 24 weeks of treatment as follows:

- AUC from a time of 0 to 24 hours post first morning dose (AUC_{0-24}) and AUC between dose interval ($AUC_{0-\tau}$)
- T_{max}
- C_{max}
- C_{trough} (concentration prior to the morning dose)

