8.5.4. Secondary Variables - PK Parameters

The PK analyses will be performed using the PK population defined above (Section 8.4). The PK parameters will be summarized and described using descriptive statistics and results placed into context with PK data from previous studies.

The following PK parameters will be derived, when appropriate and data permitting, using noncompartmental analysis methods following the morning dose at baseline (Visit 2), Week 4 (Visit 3), and EOT at Week 24 (Visit 5):

- AUC will be derived using the linear trapezoidal rule during the ascending portion of the curve and the log-trapezoidal rule during the descending portion of the curve. AUC_{0-24} after the morning dose and $AUC_{0-\tau}$ following every dose will be derived.
- C_{max}
- T_{max}
- C_{trough} (concentration prior to the morning dose)

Apparent clearance (CL/F) and $T_{1/2}$ may also be assessed, if feasible.

The PK parameters will be investigated based on frequent blood sampling. At each assessment period, blood sampling will occur at pre-dose, and 1-, 2-, 3-, and 4-hours post-dose following the morning and mid-day ataluren doses, and at pre-dose, 1-, 2-, 3-, 4-, and 12- (before the next day dose) hours after the evening ataluren dose.

Blood/plasma partitioning will be determined at 2.5 hour and 4.5 hour post morning ataluren dose at each visit.

8.5.4.1. *PK Analysis Methods*

Observed values of plasma concentrations for ataluren will be summarized at baseline (Visit 2), Week 4 (Visit 3), and EOT at Week 24 (Visit 5).

Individual PK parameters will be derived using actual sampling and dosing times. The PK parameters will be summarized with descriptive statistics at baseline (Visit 2), Week 4 (Visit 3), and EOT at Week 24 (Visit 5). (eg, n, arithmetic mean, standard deviation, standard error, median, min, and max, CV% mean, geometric mean, and CV% geometric mean). The analysis will be performed with a fully validated version of Phoenix WinNonlin V6.3 or higher.

Additional information will be provided in the PK analysis plan.

8.5.5. *Other Variables*

8.5.5.1. *Vital Signs and Physical Examination*

Vital signs (height, weight, BMI, systolic and diastolic BP, and heart rate) and physical examination data will be listed and summarized by visit and overall. Where appropriate, changes from baseline will be summarized by visit.

8.5.5.2. *Laboratory Values*

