2.3.2. Secondary Endpoints

The secondary endpoint of this study is the evaluation of PK parameters after 24 weeks of treatment as follows:

- AUC0-24 and AUC0-6
- T_{max}
- C_{max}
- Ctrough

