2.7.4. Pharmacokinetic Assessment

The PK parameters will be evaluated based on frequent blood sampling During PK assessments at baseline (Visit 2) Week 4 (Visit 3), and EOT at Week 24 (Visit 5), subjects will remain in the clinic until all blood draws are complete. At each assessment period, blood sampling will occur immediately pre-dose, and at 1-, 2-, 3-, and 4-hours post-dose following the morning and midday doses and immediately pre-dose and at 1, 2, 3, 4 and 12 (before the next day morning dose) hours post-dose following the evening ataluren dose. The PK parameters, including AUC0-24 (following the morning ataluren dose), AUC0-tau (AUC0-6 following the morning and mid-day ataluren doses and AUC0-12 following the evening ataluren doses), Tmax, Cmax, and Ctrough after each dose will be assessed.

The blood/plasma partition sampling will occur at 2.5 hour and 4.5 hour post morning dose at baseline (Visit 2), Week 4 (Visit 3), and EOT at Week 24 (Visit 5).

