7.3. Blood Pharmacokinetic Parameters

Blood PK parameters for ataluren will be estimated using non-compartmental methods with WinNonlin®. Any data points designated as anomalous values that would impact PK should be predefined before database lock if possible and identified in the report with a rationale for exclusion. The PK parameters will be estimated from the concentration-time profiles, and AUCs will be calculated using the Linear-Log Trapezoidal method (equivalent to the linear up / log down option in WinNonlin). For the estimation of PK parameters, BQL concentration following first dose at pre-dose and up to the first measurable concentration will be set to zero, BQL concentration will be set to missing otherwise. Actual sampling times, rather than scheduled sampling times, will be used in all computations involving sampling times. Actual dose will be used to calculate dose-dependent parameters. Parameters will be summarized by dose (morning, mid-day, evening) and entire day, and visits (baseline, Week 4, and EOT at Week 24). AUC0-tau and AUC0-inf for a subject at any specific dose interval will be reported as NR (not reportable) if there is one sample missing during the dose interval, and consequently the AUC0-24 for the subject at the specified day will be reported as NR.

The following blood PK parameters will be determined using non-compartmental methods as appropriate, for each visit:

Parameter	Description	Dose
C _{max}	Maximum blood concentration; determined directly from the concentration time profile; if the maximum blood concentration occurs at more than one time point, C _{max} is defined as the first maximum value	Morning, Mid- day, Evening
T _{max}	Time to C_{max} ; if the maximum value occurs at more than one time point, T_{max} is defined as the first time point with this value.	Morning, Mid- day, Evening
Ctrough	Trough blood concentration; measured blood concentration at the end of the dosing interval, directly before next administration.	Morning,

Parameter	Description	Dose
AUC ₀₋₂₄	Area under the blood concentration vs time curve (AUC) from time 0 to 24 hours post first morning dose.	Morning
AUC _{0-т}	AUC from time 0 to 6 hours post-dose following the morning and mid-day ataluren doses and AUC from time 0 to 12 hours post- dose following the evening ataluren doses. AUC from time 0 to 6 hours post-dose following the evening ataluren dose will also be calculated.	Morning, Mid- day, Evening

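### Protocol and SAP disagree on which Ctrough and which AUC are the secondary PK endpoints, and SAP section 9 declares no change

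*SAP*

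**What the plan says.** **Ctrough.** Protocol 2.2.2 makes it a secondary endpoint after 24 weeks and defines it as "concentration prior to the morning dose". Protocol 8.5.4 and the protocol's abbreviation list agree. The protocol synopsis is looser: it includes Ctrough among the parameters that "will be assessed after each dose".

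SAP 7.3 defines Ctrough as "measured blood concentration at the end of the dosing interval, directly before next administration". SAP 2.7.4 says that "Tmax, Cmax, and Ctrough after each dose will be assessed", and SAP 2.1 says the same in substance. The abbreviations under SAP Appendix 1 keep the pre-morning definition.

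**AUC.** Protocol 2.2.2 lists AUC0-24 and "AUC between dose interval" (AUC0-tau). Protocol 8.5.4 says that AUC0-tau "following every dose will be derived". SAP 2.3.2 instead lists "AUC0-24 and AUC0-6". SAP 2.1, 2.7.4 and 7.3 nevertheless define AUC0-tau as 0 to 6 h after the morning and mid-day doses and 0 to 12 h after the evening dose. SAP 7.3 adds an evening AUC0-6 as a further quantity.

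**Declared changes.** SAP section 9 states that there are none.

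**The concern.** The SAP should settle which derived value is reported under each endpoint name. Here one name covers several quantities.

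An end-of-interval Ctrough taken after each dose gives three values per PK day, at three clock times, and SAP 7.3 does not say which is the endpoint. Read literally, the value labelled as the morning-dose Ctrough is the sample just before the mid-day dose, whereas the protocol's endpoint is the sample before the morning dose. For AUC, the formal endpoint list differs from the protocol's and from the SAP's own derivation section.

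PK is the only secondary objective, and the study plans 6 to 10 subjects. Protocol 8.5.4 intends the results to be set beside PK data from previous studies, and protocol 3.2 says the earlier extension to ages 2 to under 5 years rested partly on comparable PK. A trough taken at a different clock time, or an evening AUC over half the interval, could look different from earlier data for reasons of labelling alone.

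**Working it through.** There is no stated figure to reproduce: the sample size rests on no hypothesis and the analyses are descriptive. The check compares definitions, then gives an illustrative size.

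**Step 1: which sample is the end-of-interval value?** Dosing intervals are 6, 6 and 12 h (protocol 3.3 and 5.1.2.3), and 6 + 6 + 12 = 24 h. Take the morning dose as time 0.

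| Dose | End of interval | Sample | Matches protocol Ctrough? |
|---|---|---|---|
| Morning | 6 h | pre-mid-day | No |
| Mid-day | 12 h | pre-evening | No |
| Evening | 24 h | 12 h post-evening, before next morning dose | Yes |

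Each PK day in fact has two pre-morning samples (protocol 7.3.4): the pre-dose sample at time 0 and the sample 12 h after the evening dose. At Visit 2 the first precedes any drug. At Week 24 both satisfy the protocol's wording, and neither document says which is the endpoint.

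**Step 2: which AUC differs?** For the morning and mid-day doses the interval is 6 h, so AUC0-6 is AUC0-tau. Only the evening dose differs: AUC0-6 against AUC0-12. SAP 7.3 computes both.

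**Step 3: possible size.** The documents give no half-life or absorption rate, so both are assumed: one compartment, oral, steady state, doses 10, 10, 20 at 0, 6 and 12 h, ka 0.7 to 1.5 per h, half-life 2 to 6 h. Volume and bioavailability cancel from the ratios. With ke = ln 2 / half-life, a dose D given x hours earlier contributes

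D · ka/(ka − ke) · (e^(−ke·x) − e^(−ka·x)),

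summed over all earlier doses. C6 and C12 are the values just before the mid-day and evening doses; C24 is the value before the next morning dose.

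| Half-life (h) | ka (per h) | C6/C24 | C12/C24 | Evening AUC0-6 / AUC0-12 |
|---|---|---|---|---|
| 2 | 0.7 | 3.46 | 3.82 | 0.80 |
| 2 | 1.5 | 3.86 | 4.22 | 0.86 |
| 3 | 0.7 | 1.88 | 2.12 | 0.72 |
| 3 | 1.5 | 1.97 | 2.22 | 0.77 |
| 4 | 0.7 | 1.43 | 1.60 | 0.67 |
| 4 | 1.5 | 1.48 | 1.65 | 0.71 |
| 6 | 0.7 | 1.16 | 1.25 | 0.61 |
| 6 | 1.5 | 1.18 | 1.27 | 0.64 |

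**Hand check at ka 1.5.** Absorption is practically complete 6 h after a dose (e^(−1.5 × 6) ≈ 0.0001), so each pre-dose value is proportional to the sum of D · 2^(−age/half-life), with a common accumulation factor that cancels.

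- Half-life 2 h:
  - C24 ∝ 20/64 + 10/512 + 10/4096 = 0.3345
  - C6 ∝ 10/8 + 20/512 + 10/4096 = 1.2915
  - C12 ∝ 10/8 + 10/64 + 20/4096 = 1.4111
  - Ratios: 3.86 and 4.22
- Half-life 6 h:
  - C24 ∝ 20/4 + 10/8 + 10/16 = 6.875
  - C6 ∝ 10/2 + 20/8 + 10/16 = 8.125
  - C12 ∝ 10/2 + 10/4 + 20/16 = 8.75
  - Ratios: 1.18 and 1.27

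Both agree with the table. Over the assumed range the 6 h troughs are 1.2 to 4.2 times the pre-morning value, and evening AUC0-6 is 61 to 86% of evening AUC0-12. Widening the range to half-life 1.5 to 6 h and ka 0.7 to 3 per h raises the upper ends to 7.8 (pre-mid-day), 8.2 (pre-evening) and 93%.

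**The case against.** The best defence is that nothing required by the protocol goes uncomputed. Most of it stands.

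- **AUC.** A reader of SAP 2.3.2 might infer that AUC0-tau has been replaced and the second half of the day left out. The documents do not support this. SAP 2.7.4 keeps "AUC0-12 following the evening ataluren doses), Tmax, Cmax, and Ctrough after each dose will be assessed", SAP 7.3 adds evening AUC0-6 without removing evening AUC0-12, and the AUC0-24 listed in SAP 2.3.2 covers 12 to 24 h.
- **Ctrough.** A reader might infer that the pre-morning trough will be replaced by a 6 h value. That also goes too far. On the after-each-dose reading, the evening-dose Ctrough is a pre-morning value. SAP 7.3 summarises parameters by dose and visit, and SAP 7.1 summarises concentrations by timepoint, so nothing says that the three troughs are pooled. The Dose entry for Ctrough in SAP 7.3 shows only the morning followed by a comma and looks cut off; nothing here is built on it.
- **Source of the wording.** Taking Ctrough after each dose is not the SAP's invention, since the protocol synopsis says it too.
- **Size.** The ratios rest wholly on assumed parameters. How earlier studies defined trough is not in the documents, so a biased comparison is possible but not shown.
- **Other documents.** A PK analysis plan (protocol 8.5.4) and the table shells (SAP section 11) may settle the labels. Neither is available here.

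What the defence does not answer is which Ctrough is the endpoint, why SAP 2.3.2 names a different AUC from protocol 2.2.2, and why section 9 reports no change.

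**Conclusion.** The concern holds as an unresolved inconsistency of minor severity. It is neither a clean redefinition nor a lost analysis.

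For Ctrough, the SAP attaches the endpoint's name to three values of which one is the protocol's, and it contradicts its own Appendix 1. Choosing a 6 h trough would give a value about 1.2 to 4.2 times higher. For AUC, the mismatch is confined to the endpoint list and matters only for the evening dose, where the listed quantity would be about 61 to 86% of the protocol's. Both ranges are illustrations that assume one-compartment steady state with ka 0.7 to 1.5 per h and half-life 2 to 6 h. The inconsistency between the definitions does not depend on them.

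**What to change.** In SAP 7.3, define the endpoint Ctrough as the concentration before the morning dose. State which Week 24 sample supplies it: time 0, or 12 h after the evening dose. Either meets the protocol's wording, but the choice should be fixed before database lock. Label the pre-mid-day and pre-evening values as additional troughs, and bring SAP 2.1 and 2.7.4 into line.

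In SAP 2.3.2, restore AUC0-tau (0 to 6, 0 to 6 and 0 to 12 h) and keep evening AUC0-6 as an additional parameter. If AUC0-6 is the intended endpoint, declare the change in section 9.

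The cost is SAP wording and matching labels in the table shells. No sample, visit or calculation changes.

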8. SAFETY EVALUATION

8.1. Adverse Events

Adverse events will be coded using the Medical Dictionary for Regulatory Activities (MedDRA). Adverse events will be coded to the MedDRA (Version 26.0 or higher) lower level term closest to the verbatim term. The linked MedDRA Preferred Terms (PT) and primary system organ class (SOC) are also captured in the database. The severity of AEs will be graded using the latest version of the Common Terminology Criteria for Adverse Events (CTCAE), Version 5.0.

A treatment-emergent adverse event (TEAE) during study is defined as an AE that occurs or worsens while on ataluren (on or after first dose of ataluren) up to 4 weeks after last dose of ataluren.

Only those AEs that are treatment-emergent will be included in summary tables. All AEs, treatment-emergent or otherwise, will be presented in subject data listings. An overview table of TEAEs, including number of subjects with TEAEs, treatment-emergent serious adverse events (SAEs), deaths, TEAEs classified as CTCAE Grade 3 or higher, study drug related TEAEs, TEAEs leading to study drug withdrawal will be provided. A summary table on the incidence of TEAEs by SOC and PT will be produced.

In the summary tables subjects may be counted under multiple SOCs and PTs, but for each SOC and PT, subjects are only counted once. If a subject has the same AE on multiple occasions, the highest severity (5=fatal, 4=life-threatening, 3=severe, 2=moderate, 1=mild) recorded for the event will be presented and the highest drug relationship (1 = 'Unrelated', 2 = 'Unlikely to be Related', 3 = 'Possibly Related', 4 = 'Probably Related'), reclassified into Related ('Possibly Related', 'Probably Related'), will be presented on the respective tables. Percentages are based on the number of subjects in the safety population.

8.2. Clinical Laboratory

Mean and mean change from baseline in clinical laboratory parameters listed in Table 1 will be summarized at each scheduled visit. Shift tables for laboratory parameters listed in Table 1 from baseline to each of the post-baseline visit will also be provided. Other laboratory parameters will be presented in the by-subject listings only.

Туре	Parameters			
Biochemistry	creatinine, aspartate aminotransferase, alanine aminotransferase, gamma-			
	glutamyl transferase, creatinine kinase, and cystatin C			

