7.1.6. Unscheduled Visits

An unscheduled visit may take place at any time during the study at the request of the subject's parent/guardian, or as deemed necessary by the investigator due to medical conditions. The date and reason for the unscheduled visit will be recorded. Adverse event monitoring and concomitant medications will be recorded. Other procedures and assessments will be completed as deemed necessary by the investigator and may include (but not be limited to) safety laboratory tests, electrocardiogram (ECG), vital signs, and physical examination.

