7.6.1. Definition of Adverse Events

An AE is any untoward medical occurrence associated with the use of a drug in humans, whether or not it is considered related to the drug. An AE can therefore be any unfavorable and unintended sign (including an abnormal laboratory finding), symptom, or disease in a study subject who is administered study drug in this study.

For this protocol, untoward medical occurrences that should be reported as AEs include the following:

- All AEs during the course of treatment with study drug administration
- All AEs resulting from medication misuse, abuse, withdrawal, or overdose, of study drug
- All AEs resulting from medication errors such as dispensing or administration error outside of what is described in the protocol

- Apparently unrelated illnesses, including worsening of a preexisting illness
- Injury or accidents. Note that if a medical condition is known to have caused the injury or accident (a fall secondary to dizziness), the medical condition (dizziness) and the accident (fall) should be reported as 2 separate AEs. The outcome of the accident (hip fracture secondary to the fall) should be recorded in source documents
- Abnormalities in physiological testing or physical examination findings that require clinical intervention or further investigation (beyond ordering a repeat [confirmatory] test)
- Laboratory or ECG abnormalities that require clinical intervention or further investigation (beyond ordering a repeat [confirmatory] test) unless they are associated with an already reported clinical event. Laboratory abnormalities associated with a clinical event should be captured in the source documents. Laboratory abnormalities not requiring clinical intervention or further investigation will be captured as part of overall laboratory monitoring and should not be reported as AEs

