4.5. Analysis Visits

All data analyses for this study will be performed based on nominal visits collected on the eCRF.

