8.5. Vital Signs

Mean and mean change from baseline in height, weight, and vital signs data will be summarized by visit. The hypertension status will be classified as below based on age, gender, and height-adjusted systolic or diastolic BP percentile results [Flynn 2017]. The hypertension status will be summarized by visit.

- Normal BP: BP <90th percentile for age, sex, and height; or <120/<80 mm Hg for adolescents ≥13 years old;
- Elevated BP: BP reading ≥90th percentile and <95th percentile for age, sex, and height; or 120 to 129/<80 mm Hg for adolescents ≥13 years old;
- Hypertension: BP ≥95th percentile for age, sex, and height; or ≥130/80 mm Hg for adolescents ≥13 years old.

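### The SAP's laboratory and blood-pressure tables are by visit only, with no overall or worst-value summary and no place for unscheduled values, although the protocol plans summaries by visit and overall

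*SAP*

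**What the plan says.** The SAP builds its numeric safety tables on visits:

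- SAP 4.5: "All data analyses for this study will be performed based on nominal visits collected on the eCRF".
- SAP 8.2: "Mean and mean change from baseline in clinical laboratory parameters listed in Table 1 will be summarized at each scheduled visit". Also: "Shift tables for laboratory parameters listed in Table 1 from baseline to each of the post-baseline visit will also be provided". These tables cover the six biochemistry parameters in SAP Table 1; all other laboratory parameters are listed only.
- SAP 8.5: "Mean and mean change from baseline in height, weight, and vital signs data will be summarized by visit". On blood-pressure category: "The hypertension status will be summarized by visit".
- SAP 4.1 plans by-subject listings for every eCRF domain.
- SAP 9 declares no departure from the protocol's planned analyses.

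The protocol foresees values outside the schedule and plans a wider summary:

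- Section 7.1.6 allows unscheduled visits at a parent's request or for medical reasons. Their assessments "may include (but not be limited to) safety laboratory tests, electrocardiogram (ECG), vital signs, and physical examination".
- Section 5.4.2 asks for creatinine and BUN before, and at least twice weekly during, intravenous aminoglycoside or vancomycin treatment.
- Sections 8.5.5.1 and 8.5.5.2 plan vital-sign and laboratory summaries by visit and also overall.
- Section 8.5.3 gives special attention to hepatic and renal events that lead to special diagnostic work-up.
- Section 7.6.1 makes a laboratory abnormality an adverse event if it needs intervention or further investigation, unless it belongs to a clinical event already reported. In that case: "Laboratory abnormalities associated with a clinical event should be captured in the source documents".

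**The concern.** Safety is the primary objective, and protocol 1.3.1 names renal toxicity, hepatic toxicity and hypertension with corticosteroids among the potential risks. Such changes can be short-lived. A sample taken between scheduled visits may be the only one that shows the peak.

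If the laboratory and blood-pressure tables take only scheduled visits, they can show no shift for a child whose creatinine, transaminases or blood pressure rose and recovered between visits, even though the value was measured. The renal tests requested under protocol 5.4.2 are off schedule by nature, and they too have no stated place in a table.

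**Working it through.** No stated figure needs reproducing, because the study is descriptive and has no formal sample-size calculation. The check is mainly a comparison of texts.

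**1. Where an unscheduled value can go.** The mean tables in SAP 8.2 are limited to scheduled visits. The shift tables run from baseline to each post-baseline visit. The SAP 8.5 tables are by visit. SAP 4.5 applies nominal visits to everything. No table is defined as any-time, overall or worst post-baseline, and no sentence assigns an unscheduled value to a visit. That leaves the listings in SAP 4.1, provided the value is entered in the eCRF.

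**2. What the adverse-event route covers.** SAP 8.1 counts TEAEs by system organ class and preferred term, from first dose to 4 weeks after last dose, so these tables do not depend on visits. Under protocol 7.6.1 there are three cases:

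- An abnormality that needs intervention or further investigation and stands alone is an adverse event and reaches the TEAE tables.
- An abnormality that belongs to a reported clinical event is represented by that event. For a creatinine rise during reported dehydration (the setting named in protocol 5.1.2.6), the dehydration is tabulated; the creatinine rise and its peak need not be.
- An abnormality that needs neither intervention nor investigation is left to laboratory monitoring, whose tables are those in step 1.

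In the second and third cases the size of the change can be missing from every summary.

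**3. Protocol against SAP.** Protocol 8.5.5.1 and 8.5.5.2 plan by-visit and overall summaries; SAP 8.2 and 8.5 plan by-visit only. Protocol 8.5.3 singles out hepatic and renal events; the TEAE overview in SAP 8.1 has no such line. SAP 9 declares no changes. BUN and bilirubin are measured (protocol 7.3.2) but are not in SAP Table 1, so they are listed only, even at scheduled visits.

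**4. Weight of one child.** With 6 children, 1/6 = 16.7%. With 10 children, 1/10 = 10%.

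**5. Chance drift of a worst-value table.** Post-baseline laboratory values are scheduled at Weeks 4, 12 and 24; Week 28 is a phone call. Assume three independent normal values with no true change. The expected maximum lies 3/(2√π) = 3/3.545 ≈ 0.85 SD above their mean, while a single baseline value has expected deviation 0. The mean baseline-to-worst change is therefore about 0.85 SD from noise alone, and more if unscheduled values are added.

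**The case against.** The case on the other side has several parts.

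- **A reader might infer that all safety tables depend on scheduled visits.** They do not. The primary endpoint is TEAEs, and those tables run over continuous time. The point is limited to the laboratory and blood-pressure tables.
- **A reader might infer that a transient renal or hepatic signal would be missed.** That is too strong. An abnormality that needs action is an adverse event or belongs to one, and listings for 6 to 10 children can be read in full. What can be lost from the summaries is the size of the change and the milder abnormalities.
- **A reader might turn visit spacing into a loss rate.** If an excursion lasts D days with onset uniform over 168 days, it meets one of the three draws with probability 3D/168: 3 × 7/168 = 12.5% and 3 × 14/168 = 25%. From this one might say that 75% to 88% are lost. The durations are assumptions, and the formula measures visit frequency. If no unscheduled sample is taken, there is no value for any table to recover. The figure says nothing about the effect of the SAP's rule and should not be used.
- **Exclusion is inferred.** SAP 4.5 does not say whether the eCRF has an unscheduled visit that counts as nominal, only the means sentence in SAP 8.2 uses the word scheduled, and the table shells are in a separate document. This stands as a caution, but the missing rule is itself a gap.
- **Unscheduled visits need not mean illness.** Protocol 7.1.6 also allows them at a parent's request. This stands.
- **The protocol does not define its overall summary,** so a worst-value table is not literally promised. This stands too, but the SAP has no overall summary of any kind and declares no change.

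**Conclusion.** The concern holds for the laboratory and blood-pressure tables. They are by nominal or scheduled visit, with no overall or worst post-baseline summary and no stated place for unscheduled values. The protocol plans summaries by visit and overall, and SAP 9 declares no changes. That conflict needs resolving however often unscheduled samples occur.

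The consequence is limited. The size of a transient renal, hepatic or blood-pressure change can be absent from every summary while the episode itself may be in the TEAE tables and the value in a listing. The frequency is unknown, because the documents give no expected number of unscheduled assessments. The conclusion assumes the natural reading of SAP 4.5, 8.2 and 8.5, namely that unscheduled assessments are not tabulated. The change should be made, but the primary TEAE analysis is not affected.

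**What to change.** - Keep the by-visit tables in SAP 8.2 and 8.5.
- Add to SAP 8.2, per child, the baseline-to-worst post-baseline shift and the maximum change for creatinine, cystatin C, GGT, AST and ALT, plus BUN and bilirubin, over all scheduled and unscheduled on-treatment assessments. State the time window; using the TEAE window of SAP 8.1 would align the tables.
- Add to SAP 8.5 the highest blood-pressure category and the maximum change per child, over the same assessments.
- Reword SAP 4.5 so that the nominal-visit rule governs by-visit tables only, and confirm that unscheduled results are entered in the eCRF.
- Restore the overall summaries of protocol 8.5.5.1 and 8.5.5.2, with a definition, or declare their removal in SAP 9.

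The cost is SAP wording and about two more tables, with no new procedures. There is one real downside: the worst of several values tends to exceed a single baseline by chance, by about 0.85 SD for three values under the assumptions above. Without a control arm this cannot be separated from a drug effect. The new tables should be labelled as signal detection and read alongside the by-visit tables.
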